Protocol Abstract Page

A Phase II Study of Ipilimumab PLUS Androgen Deprivation Therapy in Castrate Sensitive Prostate Carcinoma 2009-0378

Core Protocol Information

Study Chairman:	[name]
Department:	Genitourinary Medical Oncology
Full Title:	A Phase II Study of Ipilimumab PLUS Androgen Deprivation Therapy in Castrate Sensitive
	Prostate Carcinoma
Protocol Phase:	Phase II
Version Status:	Activated Closed to new patient entry as of 10/11/2013
Version:	15
Document Status:	Final

Abstract

Objectives:

Primary Objectives:

• To estimate the rate of PSA </= 0.2ng/mL at 7 months in patients treated with androgen deprivation therapy (ADT) plus Ipilimumab.

Secondary Objectives:

- To profile *immunological changes* induced in patients with metastatic prostate carcinoma treated with intermittent ADT plus Ipilimumab.
- To assess the *time to testosterone recovery* (> 50ng/mL) in patients treated with intermittent ADT plus Ipilimumab.
- To assess the *time to PD off ADT*, after treatment with intermittent ADT plus Ipilimumab.
- To characterize **safety** and drug-related adverse events of ipilimumab combined with complete androgen ablation.
- To determine the *overall survival* of patients treated with intermittent ADT and ipilimumab.

Rationale: (Be as concise as possible)

Androgen ablation induces involution of prostate cancer at both primary and metastatic sites. Androgen

ablation also leads to an accumulation of mononuclear cells within the prostate, (which is associated with a better prognosis of the disease) and the development of new seroreactivities in patients with prostate cancer. These findings suggest that the induction of specific T cell responses might contribute to the anti-tumor effect of androgen ablation. Enhancing the host immune response against the tumor might lead to an improvement in the outcome of patients with metastatic prostate carcinoma.

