- 11) Previous participation in another ipilimumab clinical trial or prior treatment with a CD137 agonist or CTLA-4 inhibitor or agonist.
- 12) History of acute diverticulitis, intra-abdominal abscess, GI obstruction, abdominal carcinomatosis or other known risk factors for bowel perforation.
- 13) Patients who do not agree to practice appropriate birth control methods while on therapy.
- 14) Concurrent use of 5-alpha reductase inhibitors (finasteride or dutasteride).

Is there an age limit? Yes

Why? Provide scientific justification:

Prostate cancer does not occur in patients under the age of 18.

[figure not shown]
Disease Group:

Prostate

[figure not shown]
Treatment Agents/Devices/Interventions:

Degarelix, Goserelin Acetate, Ipilimumab, Leuprolide Acetate

Proposed Treatment/Study Plan:

Schema: Study Phases

	Pre-study Evaluation	On-Study h Evaluation	Prior to each Dose of Ipi and every 4 weeks for 6 months after last dose of ipi	Every 12 weeks beginning 6 months after last dose of Ipi	Disease Progression (+/- 14 days of the time the patient enters on study follow- up)	Long-ter up (every after o progressi months dose
Physical Exam (interim history pertaining to current medications and treatment related toxicities)	x ^b	x	х	х	х	
CT Abd/Pelvis (preferred) or k MRI Abd/Pelvis	x ^a				х	
Chest X-ray	x ^{a,d}				x ^d	
Bone Scan	Х ^а				X	
Complete Medical History	x ^b					
Electrocardiogram	х ^b					
Height	xc					
Weight	xc					
PS (ECOG)	xc					
BP, Pulse, Temperature	xc					
Concurrent Medications	xc	х	x	х	x	
Baseline Toxicity Evaluation	x ^c					
CBC with diff. and plt.	xc	X	X	x ^j	X	
Serum Chemistry	x ^c	х	х	х	x	
Urine N-telopeptides (NTX)	x ^c	X	х	x ^j		

PSA Assessment	x ^{c,f}	X	x	X	x	
Serum Testosterone Levels	x ^{c,g}	х	x	X	x	
Autoimmune Panel	Хc					
ACTH	Х ^с	X	X	X	X	
Cortisol	xc	Х	X	X	x	
TSH	Х ^с	X	X	X	X	
Free T4	xc	X	X	x	x	
Amylase	Хc	X	X	X	x	
Lipase	xc	X	x	x	x	
SPEP and anti-TPO titer	xc	X	x	x	x	
Adverse Events			X	X	X	
Correlative Studies		X	X	X	x	
Survival						X

Legend

- a = Within 42 days of study entry +/- 3 days
- b = Within 28 days of study entry +/- 3 days
- c = Within 14 days of study entry +/- 1 day
- d = If lung metastases are evident on chest x-ray, CT of the chest should be obtained as well

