Any 2 ipilimumab related deaths unless also attributed to progression have occurred

Endpoint Definitions and Analysis Plan

For the primary analysis, the proportion of patients achieving PSA < 0.2ng/mL at 7 months will be estimated in the ITT population, along with the exact 95% confidence interval. Kaplan-Meier methods will be used to analyze the time-to-event outcomes, including:

- 1. Time to testosterone recovery: Defined as the time between day 224 of the protocol and the date at which serum testosterone returns to > 50ng/mL. As per Section 5.1, the effect of ADT should not last beyond 8 months, i.e. beyond day 224. Patients who have not achieved testosterone recovery (ie, returns to > 50ng/mL) at the last follow-up time will be treated as censoring.
- 2. Time to PD off ADT: defined as the time between day 224 of the protocol and the date of the first PSA measurement that is ≥20% above the nadir, as long as the rise is confirmed by a two additional PSA measurements separated by at least one week as described in Section 7.2. Patients who have not experienced PSA progression at the last follow-up time will be treated as censoring.
- 3. Overall survival: defined as the time between the date of registration and the date of death. Patients who have not died at the last follow-up time will be treated as censoring.

Note: For patients who experience SAEs prior to 7 months, treatment will be discontinued. However, these patients will continue to be followed-up for the efficacy assessment. They will be counted as successes for PSA response if they achieve a PSA level less than or equal to 0.2ng/ml at 7 months.

Where Will Participants Be Enrolled:

Only at MDACC

Is this an NCI-Cancer Therapy Evaluation Protocol (CTEP)?

Is this an NCI-Division of Cancer Prevention Protocol (DCP)?

Estimated Accrual:

Total Accrual at MDACC: 48
Estimated monthly accrual at MDACC: 1-2

Accrual Comments:

Do you expect your target population to include non-english No speaking participants?

Location of Treatment:

This protocol is performed on an Outpatient basis.

Length of Stay: What is the length & frequency of hospitalization?

n/a

Return Visits: How often must participants come to MDACC?

Patients will return every 4 weeks for follow-up and treatment with ipilimumab for the first 32 weeks on study. Patients will return every 4 weeks for 6 months after last dose of Ipilimumab and every 12 weeks thereafter.

Home Care: Specify what, if any, treatment may be given at home.

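### Time to testosterone recovery has no rule for ADT restart and censors deaths by implication; if the target is the proportion who actually recover, 1 minus Kaplan-Meier overstates it whenever such events are censored

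*Combined protocol and SAP*

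**What the plan says.** The Secondary Objectives include time to testosterone recovery in patients "treated with intermittent ADT plus Ipilimumab". The Endpoint Definitions and Analysis Plan states that "Kaplan-Meier methods will be used to analyze the time-to-event outcomes". Item 1 of that list sets the endpoint: "Defined as the time between day 224 of the protocol and the date at which serum testosterone returns to > 50ng/mL". The origin is justified as follows: "As per Section 5.1, the effect of ADT should not last beyond 8 months, i.e. beyond day 224". The only handling rule is "Patients who have not achieved testosterone recovery (ie, returns to > 50ng/mL) at the last follow-up time will be treated as censoring".

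Item 2 is a separate endpoint with the same origin: "Time to PD off ADT: defined as the time between day 224 of the protocol and the date of the first PSA measurement". It is not linked to item 1, and nothing says that progression leads to a second ADT course.

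In the schedule table, the row "Serum Testosterone Levels" is marked up to the disease progression visit. In the long-term follow-up column only survival is marked. Concurrent medications are also unmarked there.

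The Statistical Considerations explain the move to a single-stage design partly by the wish to use secondary-endpoint data when judging efficacy.

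**The concern.** Two events can stop a patient from recovering testosterone after the first ADT course: death, and a return to castrating therapy. Item 1 names neither. The general rule places a death without recovery among the censored observations. For restart it leaves open whether the patient is censored at that date or stays at risk. The documents do not say in so many words that restarted ADT blocks recovery. The choice of origin implies it, because the clock starts only when the ADT effect is expected to have ended.

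The censoring date is also unclear. The last follow-up time could be the last testosterone sample or the last survival contact, and the schedule lets these lie far apart after progression. If it is the last sample, patients whose sampling ends at progression are censored at an event tied to the course of their disease. If it is the last contact, patients no longer measured stay at risk as unrecovered.

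At stake are the recovery proportion and median for a named secondary objective. As written, a reader could not tell which quantity the reported curve estimates.

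**Working it through.** **What can be reproduced.** The documents give no rate, sample size or precision for this endpoint. Their only sizing figure belongs to the primary endpoint (60% against 40%, 80% power, two-sided 0.05). A one-sample normal approximation gives n = (1.960 × √0.24 + 0.842 × √0.24)² / 0.20² = 47.09, rounded up to 48, with power 80.7% at 48. That figure reproduces and is not touched by this point.

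**Direction.** At each time, 1 minus Kaplan-Meier adds the recovery hazard times the probability of not yet having recovered. The cumulative incidence adds the same hazard times the probability of having had neither recovery nor a competing event. The second probability is never larger. So 1 minus Kaplan-Meier, with competing events censored, is never below the cumulative incidence, and it lies above it once any such event precedes later recoveries.

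**Size (all rates assumed).** Take constant, independent hazards from day 224:
- recovery hazard λ = ln 2 / m, where m is the median time to recovery;
- competing hazard κ = λ × c / (1 − c), where c is the share of patients whose first event is death or restart;
- 1 − KM(12) = 1 − exp(−12λ);
- CIF(12) = λ/(λ + κ) × [1 − exp(−12(λ + κ))].

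Example with m = 6 and c = 20%: λ = 0.1155 and κ = 0.0289 per month. Then 1 − KM(12) = 1 − exp(−1.386) = 75.0%, and CIF(12) = 0.80 × [1 − exp(−1.733)] = 65.9%.

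| Median recovery (months) | 1 − KM at 12 months | CIF, c = 2% | 5% | 10% | 20% | 30% |
|---|---|---|---|---|---|---|
| 4 | 87.5% | 86.3% | 84.4% | 81.1% | 74.1% | 66.4% |
| 6 | 75.0% | 74.2% | 72.9% | 70.7% | 65.9% | 60.3% |
| 9 | 60.3% | 59.8% | 59.1% | 57.8% | 54.8% | 51.3% |
| 12 | 50.0% | 49.7% | 49.2% | 48.3% | 46.4% | 44.0% |

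The gap runs from 0.3 points (m = 12, c = 2%) to 21 points (m = 4, c = 30%).

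**The other target.** Suppose the quantity wanted is recovery had ADT not been restarted. If restart is independent of recovery, censoring at restart is unbiased: simulation gives 75.0% against a true 75.0%. Dependence was simulated with two equal groups, one nine times as prone to restart as the other and with half or twice the other group's recovery hazard. At nominal competing shares of 10%, 20% and 30%:
- restart-prone patients recover more slowly: 63.2%, 64.1% and 65.6% against true values of 62.4%, 62.4% and 62.6%, a bias of +0.8 to +3.0 points;
- restart-prone patients recover faster: 83.9%, 83.2% and 82.5% against a true 84.4%, a bias of −0.5 to −1.9 points.

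**If restarters stay at risk.** If they are followed to a later contact without being censored, the curve moves toward the cumulative incidence and understates recovery while off ADT.

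**The case against.** The strongest reply is that bias needs a target. If the trial wants recovery after one ADT course in the absence of a second, Kaplan-Meier censored at restart is a legitimate estimator, and under independence it is exactly right. That stands, so a reader who infers that the recovery curve is biased outright goes further than the documents allow. Existence, direction and size all depend on the target, on the meaning of last follow-up, and on how many patients die or restart before recovery.

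Several other tempting inferences also fail:
- **Very large gaps.** Median times to restart of 24, 12 and 6 months, against a 6-month median recovery, would give 66%, 58% and 47% instead of 75%. The arithmetic is correct. But these medians mean that 20%, 33% and 50% of patients restart before recovery, which nothing in the documents supports, and they presume a censor-at-restart rule that the plan does not state.
- **That patients will restart before recovery.** Intermittent ADT makes re-treatment foreseeable, but no restart criterion, frequency or timing is given. Progression in item 2 needs a rise of at least 20% above nadir confirmed by two further measurements, and it is not described as a trigger for ADT.
- **That the curve will mix two ADT courses.** Testosterone is not marked after the progression visit, so a recovery after a later second course would usually go unobserved.

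It is also fair to say that the gap may be small beside sampling error. At c = 10% and a 6-month median it is 4.3 points, while the 95% half-width at 75% with 48 patients and no censoring is 1.96 × √(0.75 × 0.25 / 48), about 12 points. But that error is reported with the estimate, whereas a choice between targets that the plan never makes is invisible to the reader. Finally, a rule may exist in Section 5.1 or 7.2. The finding is limited to the available text.

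**Conclusion.** The point holds in conditional form. The available text has no rule for ADT restart, censors deaths only by implication and leaves the censoring date open, so the quantity estimated is undefined. If the target is the proportion who actually recover, censoring death or restart makes 1 minus Kaplan-Meier too high. With an assumed 6-month median and 2% to 30% competing first events, 75% at 12 months stands for about 74% to 60%. This is a range under constant independent hazards, not an estimate for this trial. If the target is recovery without restart, the method depends on an independence assumption that the plan neither states nor justifies.

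The change is worth making because it is standard and cheap, and because the plan relies on its secondary endpoints to help judge efficacy. The endpoint is nevertheless descriptive, in a single arm, with no test or decision rule attached.

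**What to change.** Amend item 1 of the Endpoint Definitions and Analysis Plan to:
- name the target as first testosterone recovery after day 224, reported as a cumulative incidence (Aalen-Johansen);
- treat death and restart of castrating therapy before recovery as competing events;
- show Kaplan-Meier censored at restart as a sensitivity analysis, with its independence assumption stated;
- set the censoring date for patients with no event at the last testosterone measurement.

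Add the date of ADT restart to data collection, because the schedule does not mark concurrent medications in long-term follow-up and the date may otherwise be lost after progression. If Section 5.1 or 7.2 already contains a rule, cite it in item 1 and reconcile the two.

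The cost is a few sentences, standard software and one additional date per patient. The reported recovery proportion may be lower than the Kaplan-Meier figure. No clinical rule for restarting ADT is proposed.

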- e = Must include: creatinine, BUN, sodium, chloride, CO2, potassium, calcium, magnesium, phosphorus, glucose, albumin, total protein, total bilirubin, SGOT [AST], SGPT (ALT), alkaline phosphatase, bone alkaline phosphatase (ALP) and LDH
- f = for patients registered after initial androgen ablation, PSA must have been assessed within 3 weeks prior to androgen ablation initiation and that will be considered as baseline
- g = for patients registered after initiation of androgen ablation serum testosterone levels are preferable within 3 weeks prior to initiation of androgen ablation, though lack of this information will be acceptable for these patients
- h = On study tests/visits that must occur within a defined time frame shall have a standing window of allowance that is equal to +/-2 days for any laboratory testing
- i = Adverse events will be monitored using the NCI CTCAE Version 3.0
- j = Bone alkaline phosphatase and urine N-telopeptides (NTX) at Week 25 (month 7)
- k = Restaging scans or other disease assessment diagnostics during study are at the discretion of study collaborator or the principal investigator and shall be performed if disease progression is suspected
- I = 90mL of peripheral blood will be collected and may be banked for future research related to immunologic response

Table 2. Regimen Description.						
Agent	Dose	Route	Schedule	Duration		
LHRH Analogue (one of the following) or Antagonist						
Leuprolide	7.5mg*	IM	Once a month*	8 months		
Goserelin	3.6mg*	SC	Once a month*	8 months		
Degarelix	80mg	SC	Once a month	8 months		
2. Ipilimumab						
	10mg/kg	IV over	Once every 4			
		90 min**	weeks x 4			

^{*} Leuprolide 22.5mg or Goserelin 10.8mg every 3 months can be used for ADT as long as the total duration of ADT does not exceed 8 months. For example, a 3-month depot formulation can be used for the first six months, followed by two 1-month depot formulations, to complete 8 months of ADT.

Statistical Considerations:

This is a single arm phase II trial to evaluate the rate of PSA \leq 0.2ng/mL in patients treated with ADT plus Ipilimumab. The primary endpoint is the proportion of patients achieving a PSA \leq 0.2ng/mL at month 7.

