The trial was originally designed to use a Simon's optimal two-stage design to stop the trial if 7 or less among the first 16 patients achieved a PSA \leq 0.2ng/mL at month 7. However, since then ipilimumab has been approved by the FDA for use in melanoma patients and there are data showing that the full effect of immunotherapies can take many months (possibly longer than 7) to become evident. On the other hand, the accrual rate for this trial has been faster than we originally expected. Since its activation on 06/17/2011, we have already enrolled 9 patients. Given the fast accrual rate and the desirability of a longer wait time and of data from the secondary endpoints to reliably assess efficacy, we now propose to change the study to a single-stage design for efficacy endpoint. Based on new safety data obtained since the trial was first designed, the safety monitoring plan has also been changed as described below. We will perform a final analysis on the primary and secondary efficacy endpoints when the study is complete.

Let S be the event of achieving PSA \leq 0.2ng/mL at month 7. It is assumed that ADT plus Ipilimumab will have a target rate of 60% for S. A rate of 40% or lower is considered a failure and the combination therapy will be rejected under this circumstance. With a sample size of 48 patients, we will have an 80% power to detect such a 20% difference using a Chi-squared test and with a two-sided type I error rate of 0.05. The sample size was computed using nQuery Advisor 7.0.

Safety Monitoring and Rules:

The PI will meet with the research nurse and data coordinator regularly to monitor toxicity events. Toxicity reports will be generated monthly and reviewed by the PI and the statistician. If at any time during the study, one of the following criteria is met, then accrual will be suspended until the PI has reviewed the events and determined the appropriate course of action, which could include a protocol amendment to decrease the dose of ipilimumab.

- ≥ 40% of subjects treated on the ipilimumab arm develop a ≥ Grade 3 toxicity thought to be related to the ipilimumab.
- > 10% of subjects experience an ipilimumab related > Grade 3 toxicity that cannot be alleviated or controlled by appropriate care and/or steroid and/or infliximab therapy within 14 days of the initiation of such therapy

^{**} Ipilimumab administration will be allowed a standing window for completion of the infusion +/- 10 minutes of targeted time.

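### The SAE note leaves open whether ADT is stopped, and the fixed day-224 origin mistimes both off-ADT endpoints for any patient whose ADT cover ends earlier

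*Combined protocol and SAP*

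**What the plan says.** All references are to the combined protocol and SAP.

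- **Note on SAEs** (end of Endpoint Definitions and Analysis Plan): "For patients who experience SAEs prior to 7 months, treatment will be discontinued". It goes on: "However, these patients will continue to be followed-up for the efficacy assessment". On scoring: "They will be counted as successes for PSA response if they achieve a PSA level less than or equal to 0.2ng/ml at 7 months".
- **Treatment Agents/Devices/Interventions**: degarelix, goserelin and leuprolide are listed together with ipilimumab.
- **Table 2, Regimen Description**: ipilimumab is given every 4 weeks for four doses, and the LHRH agent for 8 months. The footnote allows 3-month depots "as long as the total duration of ADT does not exceed 8 months". Its example is 3-month depots for six months, "followed by two 1-month depot formulations, to complete 8 months of ADT".
- **Endpoint Definitions, items 1 and 2**: both off-ADT times run from day 224. The reason given is that "the effect of ADT should not last beyond 8 months, i.e. beyond day 224".
- **Inclusion 3**: patients already on ADT may enter up to 1 month after starting it, provided total exposure does not exceed 8 months.
- **Schema legend j**: month 7 is week 25.

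**The concern.** There are two linked problems.

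The first is an undefined word. *Treatment* could mean ipilimumab, ADT or both, and the note covers any SAE up to 7 months. Once the four ipilimumab doses have been given, a reader who applies the note literally finds only ADT left to stop. That would cut short the course in Table 2 for an event that may be unrelated to study drug.

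The second does not depend on how the first is resolved. The off-ADT endpoints measure time since ADT stopped acting, but they are timed from a common protocol day. The analysis plan has no provision for cover that ends before that day. Such a patient's time is recorded too short. If testosterone recovers or PSA rises before day 224, the time is negative, which a Kaplan-Meier analysis cannot accept. Setting it to zero or dropping the patient would move the estimate in opposite directions, and the plan chooses neither.

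**Working it through.** **1. The plan's own figures.** 8 × 28 = 224, so day 224 is the end of the eighth 28-day month (32 weeks). Week 25 begins on day 24 × 7 + 1 = 169. For the sample size, a one-sample test of 40% against 60% (two-sided 0.05, 80% power) gives

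n = (1.960 × √0.24 + 0.842 × √0.24)² / 0.20² = 47.09, rounded up to 48.

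Power at 48 is 80.7%. The stated N reproduces, and nothing below changes it.

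**2. When ipilimumab ends.** The week of the last dose is the week of the first dose + 12. The week of the first dose is not stated, so it is an assumption here.

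| First dose (week) | Last dose (week) | Weeks from last dose to week 25 |
|---|---|---|
| 1 | 13 (day 85) | 12 |
| 5 | 17 | 8 |
| 9 | 21 | 4 |
| 13 | 25 | 0 |

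The Return Visits text, "Patients will return every 4 weeks for follow-up and treatment with ipilimumab for the first 32 weeks on study", does not sit easily with four 4-weekly doses and does not settle the start week.

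**3. The two readings of the note.**
- *Treatment* includes ADT: an SAE before month 7 can end ADT early, against the 8 months in Table 2.
- *Treatment* means ipilimumab: the note has no effect after dose four, ADT continues, and Table 2 is not contradicted.

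**4. The clock error.** Let E be the protocol day on which ADT cover ends and T the true time from E to the event. The plan records T − G, where G = 224 − E. The result is negative whenever T < G.

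- *Inclusion 3, no SAE needed.* Assume protocol days count from study entry and ADT began 1 month earlier. In the plan's 28-day months, E is at most 224 − 28 = 196, so G is at least 28 days for that patient. In calendar months, 8 months less 1 month is 243.5 − 30.4 = 213.1 days, so G is about 11 days. Patients who began ADT less than 1 month before entry have a smaller G.
- *Early stop, 1-month depot.* Assume ADT starts on day 1 and the last injection is on day 85. Then E = 85 + 28 = 113 and G = 111 days, about 16 weeks. The month-7 PSA falls 169 − 113 = 56 days after cover ended.
- *Early stop, 3-month depot.* With the same last injection, E = 85 + 84 = 169 and G = 55 days, about 8 weeks. Cover lasts to the month-7 PSA (169 − 169 = 0 days).

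**5. Month-7 response, illustration only.** The documents give neither an SAE rate nor a response rate after early ADT stop. If a fraction f stops ADT and responds at rate r, the overall rate is 0.60 − f × (0.60 − r). Let r range from 0 to 30%.

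| f | Overall rate | Approximate power, N = 48 |
|---|---|---|
| 5% | 57 to 58.5% | 67 to 74% |
| 10% | 54 to 57% | 51 to 67% |
| 20% | 48 to 54% | 21 to 51% |

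This arises only if *treatment* includes ADT. It overstates the loss for patients still covered by a depot, or stopped close to month 7.

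**The case against.** The strongest reply is that the note was meant for ipilimumab. The accrual-suspension criteria are about ipilimumab toxicity, and the Return Visits text uses *treatment* in that sense. The supplied text is also a protocol abstract. It cites Sections 5.1 and 7.2, which it does not include, and patient-level stopping rules may be set out in the full protocol. This stands: the note is ambiguous and is not shown to contradict Table 2. A reader might infer that after week 13 the note can only stop ADT. The documents do not support that, because on the ipilimumab reading the note simply lapses, and week 13 itself rests on an assumed first dose in week 1.

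Three other inferences also fail.
- A conflict with the safety rules. Those rules, including the one on toxicity that "cannot be alleviated or controlled by appropriate care and/or steroid and/or infliximab therapy within 14 days", decide when accrual is suspended. The note concerns individual patients, so a difference in scope is not a contradiction.
- Different practice between sites. Enrolment is at one centre.
- An undefined primary endpoint. Analysis is by ITT, follow-up continues, and each patient is scored on the actual month-7 PSA.

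It can also be said that day 224 reflects a ceiling on ADT and does not assert that everyone completes 8 months, so a fixed origin is a convenient approximation. The first part is fair. It does not rescue the origin, because a ceiling allows cover to end earlier and those are the patients who are mistimed.

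**Conclusion.** The point holds in two parts of different strength.

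The SAE note is an ambiguity to be reconciled with Table 2. It conflicts with the 8-month course only if *treatment* includes ADT.

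The day-224 origin is an error for any patient whose ADT cover ends before that day, however the note is read. For a patient who enters 1 month into ADT it is about 11 to 28 days, depending on how months are counted, provided protocol days run from study entry. After an early stop it depends on the depot: 55 to 111 days in the examples, which assume ADT from day 1 and a last injection on day 85. How many patients are affected cannot be known from the documents.

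A reader might go further and infer a material loss of power for the primary endpoint. The documents do not support a figure: the SAE rate and the response after stopping are both unknown, and some depots cover the patient to month 7.

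**What to change.** 1. Reconcile the SAE note with Table 2 by stating which agent or agents it applies to and which SAEs it covers. Which rule applies is for the sponsor and the investigator to decide. The Return Visits sentence should be aligned with the four-dose schedule at the same time.
2. Start time to testosterone recovery and time to PD off ADT at each patient's actual end of ADT cover, taken as the last LHRH dose date plus the depot's duration. Keep the day-224 origin as a sensitivity analysis. State how an event before the end of cover is handled, since it would precede either origin.
3. Report how many month-7 PSA results were obtained after an early ADT stop.

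The cost is an amendment to two secondary endpoint definitions, a clarified note and one listing. LHRH dose dates and formulations are needed. The documents do not say that they are recorded, so this is assumed. The study is closed to new entry, so items 2 and 3 carry most of the remaining value. The month-7 primary endpoint and N = 48 stay as they are.

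### Testosterone draws become 12-weekly soon after the recovery clock starts, but only Kaplan-Meier is planned; add an interval-censored report of time to testosterone recovery

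*Combined protocol and SAP*

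**What the plan says.** Two secondary endpoints share a starting point, set out in Endpoint Definitions and Analysis Plan:

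- Time to testosterone recovery: "Defined as the time between day 224 of the protocol and the date at which serum testosterone returns to" above 50 ng/mL.
- Time to PD off ADT: "defined as the time between day 224 of the protocol and the date of the first PSA measurement" at least 20% above nadir, with confirmation.

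The same section names the method: "Kaplan-Meier methods will be used to analyze the time-to-event outcomes". The only censoring it describes is at last follow-up, for patients without the event.

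The visit schedule is tied to ipilimumab, not to the end of ADT. Return Visits first says "Patients will return every 4 weeks for follow-up and treatment with ipilimumab for the first 32 weeks on study" (week 32 is day 224), and then "Patients will return every 4 weeks for 6 months after last dose of Ipilimumab and every 12 weeks thereafter". The Schema: Study Phases table has a matching column, "Every 12 weeks beginning 6 months after last dose of Ipi", in which both the PSA and the testosterone rows are marked. Table 2 gives four ipilimumab doses, one every 4 weeks.

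**The concern.** The sampling interval triples shortly after the testosterone clock starts. A 12-weekly draw can only bracket the day on which testosterone passed the threshold. Plain Kaplan-Meier puts the event at the far end of that bracket, so visit spacing is added to the reported time and reads as slower recovery.

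Time to testosterone recovery is a named secondary objective. Statistical Considerations also gives the need for secondary-endpoint data as one reason for moving to a single-stage design. A reader who takes the Kaplan-Meier median at face value, or sets it against data collected on another schedule, would be misled by some weeks.

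**Working it through.** **Plan's own figure.** The documents give no expected median, precision or power for this endpoint, so there is nothing to reproduce on the point itself. The 48 patients used below do reproduce from the primary endpoint: (1.960 + 0.842)² × 0.24 / 0.20² = 47.1, rounded up to 48.

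**When draws become 12-weekly.** The fourth dose is 3 × 28 = 84 days after the first. The switch, counted from day 224, is first-dose day + 84 + length of 6 months − 224. The first-dose day and the length of 6 months are assumptions.

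| First dose | 6 months | Switch after day 224 |
|---|---|---|
| day 1 | 168 days | 1 + 84 + 168 − 224 = 29 days (about 4 weeks) |
| day 1 | 182 days | 43 days (about 6 weeks) |
| day 29 | 168 days | 57 days (about 8 weeks) |
| day 29 | 182 days | 71 days (about 10 weeks) |

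A patient stopped after one dose reaches the 6-month point 55 to 13 days before day 224. After two doses it falls between 27 days before and 15 days after. These patients have little or no 4-weekly sampling on this clock.

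**Rough size.** An event spread evenly over a gap is found half a gap late: 84/2 = 42 days, or 6 weeks, on 12-weekly draws, against 28/2 = 14 days, or 2 weeks, on 4-weekly draws. The laboratory window ("standing window of allowance that is equal to +/-2 days for any laboratory testing") is small against 84 days.

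**Simulation.** There were 48 patients, with Weibull times from day 224 (shapes 1 and 2), draws exactly on schedule, no unscheduled draws and no censoring. The shift is the Kaplan-Meier median at detection dates minus the Kaplan-Meier median of the exact times in the same data. Three grids had draws at days 1, 29, 43; 1, 29; and 1, 29, 57 after day 224, each then every 84 days.

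| Assumed true median (weeks) | Average shift (weeks) |
|---|---|
| 8 | 4.9 to 10.0 |
| 12 | 4.3 to 8.2 |
| 16 | 3.3 to 5.5 |
| 20 | 5.4 to 7.9 |
| 26 | 4.5 to 6.5 |
| 39 | 5.3 to 6.1 |
| 52 | 5.9 to 6.2 |
| 4-weekly draws throughout | 1.7 to 2.1 |

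**Where the shift is small.** On a fourth grid with the latest switch (draws at 1, 29, 57, 71, then every 84), a true median of 8 weeks gives only 1.0 to 2.2 weeks, because it lies before the switch. At 26 weeks that grid reaches 7.4. Medians of 2 to 3 weeks give 1.2 to 2.2 on all four grids.

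**Single trial.** For medians of 26 to 52 weeks, the Kaplan-Meier shift in one trial of 48 runs from about 0.4 to 11.5 weeks (5th to 95th percentile).

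**Interval-censored alternative.** On the same data (first three grids) the interpolated Turnbull median was off by 0.1 to 1.8 weeks on average. In a single trial its error is about 3 weeks either way for medians of 26 to 52 weeks; the widest range seen, 5th to 95th percentile, was about −2 to +6.

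**Sensitivity.** With follow-up ending between 52 and 156 weeks after day 224 (assumed), the average shift is 4.3 to 6.4 weeks for Kaplan-Meier and 0.3 to 1.9 for Turnbull. With 40% stopping early (assumed), it is 4.6 to 8.2 and 0.2 to 1.4. A Weibull interval-censored fit was off by 0.1 to 1.7 weeks when the truth was Weibull but 1.5 to 4.7 when it was log-normal, so Turnbull should lead.

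**The case against.** The strongest objection concerns time to PD off ADT, and it stands. A reader might infer that both off-ADT medians are biased. The PD definition ends at the first qualifying PSA measurement, so the detection date is the event date and Kaplan-Meier estimates exactly what is defined. An interval-censored analysis there would target a different quantity, the unobserved crossing. The testosterone definition differs: it names the date the level returns, not the date of a measurement.

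Other points in the plan's favour:

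- *No median is promised.* True. With a shared grid and no missed visits, the Kaplan-Meier proportion at each visit date is right, and only the placing of the drop between visits is late. But a median is the usual summary of such a curve, and it is the one affected.
- *Event-driven tests fill the gap.* Legend item k says that restaging or other disease assessments "shall be performed if disease progression is suspected". That concerns progression, not testosterone recovery.
- *Turnbull only brackets the median.* True: the bracket is about 12 weeks wide when patients share a grid, and the interpolated value assumes events spread evenly within it.
- *Sampling scatter is as large.* With exact times and 48 patients, the median already varies by about ±4.5 to ±9 weeks at 26 weeks and ±8 to ±18 at 52. This limits the importance, but the shift always goes one way and scatter does not.
- *Some text is not available.* The endpoint section cites Sections 5.1 and 7.2, which are not in the text supplied, so any added sampling rule there could not be checked.

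**Conclusion.** The point holds for time to testosterone recovery, as a minor one. Its size is conditional. If the true median falls after the switch to 12-weekly draws, the Kaplan-Meier median is on average about 3 to 10 weeks late, typically about 6. If it falls before the switch, the figure is about 1 to 2 weeks, which 4-weekly draws would give anyway. The timing rests on an assumed first dose between day 1 and day 29 and on 6 months taken as 168 to 182 days. The shifts rest on assumed medians and event-time shapes, because the documents state none.

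Two stronger readings are not supported. One is that the medians will certainly be late by several weeks: without an expected median, nobody can say on which side of the switch it falls. The other is that the trial's efficacy conclusion is inflated: the rejection rule uses only PSA at month 7, and the two off-ADT times carry no test, threshold or comparator.

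**What to change.** Keep Kaplan-Meier and add an interval-censored report of time to testosterone recovery. Each patient's interval runs from the last draw at or below 50 ng/mL to the first draw above it, on actual draw dates; patients never above it are censored at their last draw. Use the Turnbull estimator, give the median as an interval with its interpolated value, and state that interpolation assumes an even spread within the gap.

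For time to PD off ADT, keep Kaplan-Meier as the analysis and describe its median as time to detection under mainly 12-weekly sampling. An interval-censored version is optional, as a sensitivity analysis.

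The cost is a little extra analysis and a median that looks less precise (and, if the PD option is taken, less favourable). It needs no new visits or patients and remains possible with enrolment closed.

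Extra 4-weekly draws are not recommended. Continued for 6 months from day 224, they would cut the average Kaplan-Meier shift to 1.7 to 3.0 weeks for assumed medians of 8 to 20 weeks but leave it at 5.7 to 6.8 for medians of 26 to 52. They would add patient burden without reliably solving the problem.
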